## **7.5. Discontinuation/Withdrawal of Participants from Study**

Each participant has the right to withdraw from the study at any time. In addition, the Investigator may discontinue a participant from the study at any time if the Investigator considers it necessary for any reason including:

- New diagnosis of other serious medical or mental health condition that significantly impacts on quality of life.
- Withdrawal of Consent

Withdrawal from the study will not result in exclusion of the data for that participant from analysis, as these data will provide information regarding feasibility of use of the SCQOLIT in dermatology clinics. The reason for withdrawal will be recorded on the CRF. Withdrawn participants will not be replaced. If a withdrawing patient requests data to be excluded and/or destroyed this request will be adhered to. This has also been documented in the PIS.

## **7.6. Definition of End of Study**

The end of study is the date of the last visit / telephone follow-up / interview of the last participant.

## **8. STUDY DATA COLLECTION**

The data collected in this study are two quality of life questionnaires – the SCQOLIT tool (Appendix C) and the EQ-5D (Appendix D), which will be printed on double-sided paper. These will be administered according to the schedule detailed in Appendix A. All patients will be designated a Questionnaire - Unique reference number (Q-URN) by the CI and this will be used on all questionnaires (rather than names or initials).

**For Group 1** – Study questionnaires will be sent in a separate sealed envelope with the diagnosis letter to patients who have consented to the study. These will be completed at home and returned by post in a pre-paid envelope. A covering letter will be sent to patients explaining what they need to do [see example Covering letter]. The Chief Investigator will review all responses and if they are concerned that the patient has significant impairment of their QOL, then as part of the standard duty of care to these patients, the Chief Investigator will contact the patient to assess this further and arrange follow-up in the clinic or with the Skin Cancer Nurse Specialist as deemed clinically required.

**For Group 2** – Study questionnaires will be completed in the clinic. The questionnaires will be completed by the patient on their own and then reviewed by clinicians who are involved in the direct care of the patient and the scores will be calculated in the clinic. This has been agreed by Dermatology clinical staff at the Clinical Governance meeting (15th July 2014). Any specific high-scoring items identified will be discussed with the patient at the time. Any specific issues identified from the questionnaires will allow for open dialogue with the clinician. If there is sufficient concern that the patient has significant QOL impairment (score greater than 20/30 or any specific item scoring highly e.g. concerns about dying) then the patient will be referred to the Skin Cancer Nurse Specialist, as would be carried out as part of the standard care pathway for patients who are deemed to be significantly anxious or concerned about their diagnosis. This process is important as clinical staff will then be able to feedback at the focus group in the Dermatology Departmental Clinical Governance Meeting, regarding unmet needs and unidentified patient concerns. Any action taken by the clinicians will be reported to the CI and recorded on the CRF.

**Group 3: Interviews** – Twenty patients from Groups 1 and 2 will be interviewed by the Co-investigator (Qualitative Researcher). This will take place after three to six months from date of entry into the study, for individuals who volunteer to be contacted by the Qualitative Researcher. The interview will be undertaken at a time convenient to the patient when they attend Dermatology Outpatients for a follow-up appointment. All interviews will be recorded using Olympus DSS digital recorder and transcribed verbatim by the researcher. Data will be anonymous and identified by an Interview unique reference number (URN). The interview URN (I-URN) will be different to the Questionnaire study URN (Q-URN) so that the data cannot be linked. Participants will not be identified in any report. Only their gender and from which group they have been recruited from (i.e. Group 1 or 2 from the Questionnaire study) will be recorded. Patient consent forms, interview recordings and transcripts will be stored securely in locked cabinets/drawers at the University of Oxford. Electronic details will be encrypted and stored on password-protected University of Oxford computers. The Chief Investigator will have access to these data and there will be a filenote in the Research Study Master File stating where the data is being stored.

**Group 4: Focus Group (Clinicians)** – Approximately 10 – 15 Dermatology clinical staff will be invited to attend focus group work to establish staff preferences, views and experiences of collecting PROMs data in a clinical setting. Their gender and role (Doctor or other) will be recorded. All focus group work will be recorded using Olympus DSS digital recorder and transcribed verbatim by the researcher. Data will be anonymous and unidentifiable and when published will not be able to be traced back to any individual. Data will be stored on password-protected computers in the University of Oxford.

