Demographic details (age, gender, Fitzpatrick skin type) and clinicopathological information (skin cancer type, histological subtype, site, tumour diameter, previous history of skin cancer, active current medical conditions, medication history) for all study participants will be recorded so this information can be correlated with the participant questionnaire scores. Subgroup analysis of scores will also be undertaken.

**Group 3 (Interviews):** A Qualitative Researcher (Co-Investigator) will undertake structured interviews with approximately 20 patients from both Group 1 and 2. Potential participants will be invited to volunteer their contact details at the time of consent to the Questionnaire study. This is optional; they may refuse to do so and still take part in the main questionnaire study. The patient will then be contacted by the Qualitative Researcher (Co-Investigator) at a later date and subsequently consented for the interview. Consent can take place on the telephone (details provided in section 7.1) but this will be

confirmed face-to-face in written form when the patient attends the Dermatology department for the interview.

**Group 4 (Clinician focus group):** As part of clinical governance arrangements, monthly Dermatology Departmental Clinical Governance meetings are held with staff (including Dermatology doctors, Dermatology nurses, Dermatology healthcare assistants and Skin Cancer Nurse Specialists) to discuss service improvement issues. Preliminary discussion on 15th July 2014 (approx. 20 attendees) confirmed engagement and willingness of the Dermatology clinical team to support the project. We aim to discuss the project at the end of the study period in the same setting, to establish staff perspectives on the study, to establish usefulness of the SCQOLIT tool and to identify any barriers to implementation. Staff will be provided with [PIS 4: Focus group] and invited to consent to the focus group work using Consent Form – Focus Group (Clinicians).

Mixed methods will be used to evaluate the acceptability of the SCQOLIT tool as a process of PROM data collection in the Dermatology clinic (detailed in section 9).

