**Group 3 (Interviews):** The Qualitative Researcher (Co-Investigator) will undertake structured interviews with 20 patients randomly selected from both Groups 1 and 2. Patients will be invited to voluntarily provide their contact details at the time of initial consent to the main Questionnaire study using a separate ‘Contact Interview Form’. Patients will be advised at this time that they may not necessarily be contacted at a later date if they are not selected for the Interview study. The contact details of the patients will be stored by the CI and once patients are entered into the questionnaire study, their details will then be sent securely to the Qualitative Researcher. The randomly selected patients will subsequently be contacted by the Qualitative Researcher (Co-Investigator) who will invite patients to participate by posting the separate Patient Information Leaflet: Group 3 (Interviews) and consent form (Consent Form – Interviews) to them. Patients will be allowed sufficient time to review the PIS. They will be provided with the Qualitative Researcher’s contact details and the CI contact details on the PIS, if they have any queries. The patient will be contacted by telephone by the Qualitative Researcher and a mutually agreed interview date will be arranged once the patient has consented verbally on the telephone. At the beginning of the face-to-face interview the Qualitative Researcher will confirm that the patient is happy to proceed and record written consent [Consent form – Interviews] to enter this part of the study. The patient will be offered the option to withdraw at this point if they decide to do so.

**Group 4 (Focus Group – Clinicians):** Clinicians who work in the Dermatology Department, have direct care responsibilities for patients with NMSC and who have been involved with the study will be invited to

consent to a focus group and be provided with a PIS 4: Focus Group (Clinicians). This will take place as part of a monthly Dermatology Clinical Governance Meeting.

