### **7.4. Subsequent Visits**

Following the participant's informed consent to participate in the study and confirmation of their eligibility (i.e. histological diagnosis of NMSC confirmed\*), patients will be asked to complete a SCQOLIT and EQ-5D questionnaire according to the study schedule (Appendix A) at visit numbers:

- 1) Baseline visit
  - a) by post if patient is given their diagnosis by post (Group 1 – considered low risk skin cancer group as determined from Oxford Skin Cancer MDT guidelines)
  - b) or face-to-face when the diagnosis is given in clinic (Group 2 – considered moderate – high risk skin cancer group as determined from Oxford Skin Cancer MDT guidelines)
- 2) At 3 months follow up
  - a) postal, for those patients discharged to community care, deemed 'low risk' (Group 1)
  - b) or face-to-face if the patient is returning to the dermatology clinic for routine follow-up (Group 2 – high risk skin cancer)
- 3) At 6 – 9 months in the Dermatology clinic if the patient is deemed high risk i.e. squamous cell carcinoma with high risk clinicopathological features (denoted by the National BAD Multidisciplinary Guidelines for management of SCC) or rare NMSC (Group 2 only – See Appendix B).

\* Participants will be entered into the study and should have completed the baseline questionnaire within three weeks of the date that they were informed of their diagnosis of NMSC (not date of pathological diagnosis).

There will be no additional visits to the clinic required for any aspect of the questionnaire study. The timeline for administering questionnaires in the clinic has been set according to the standard care pathway for these patients. This reflects routine clinical practice and the feasibility study is designed to run as close as possible to the standard pathway of care.

Participants will also receive a reminder telephone call from the Chief Investigator about each questionnaire once they receive them in the post to maximize response rates. This will occur 10-14 days after the questionnaires have been posted.

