**Structured interviews (Group 3)** will be undertaken after three to six months from date of entry into the study, for individuals who volunteer to be contacted by the Qualitative Researcher. Twenty individuals who have participated in the study from both Groups 1 and 2 will be invited to attend. Patients who volunteer their contact details will be informed that only 20 patients will be chosen at random for an interview. This is also written on the consent to provide details form. Patients will be contacted at random until 10 patients from Groups 1 and 2 have completed an interview. The interview will be undertaken at a time convenient to the patient in the Dermatology Outpatient Department.

**Group 4: A clinician focus group** will be undertaken to establish staff preferences and views regarding the study methodology and the SCQOLIT tool. This will be led by the Qualitative Researcher and supported by the Chief Investigator and will take place as part of the regular monthly Dermatology Departmental Clinical Governance meetings, which are undertaken to discuss service evaluation issues. It will involve 10 – 15 clinicians including Dermatology doctors, Dermatology nursing staff, skin cancer nurse specialists and health care assistants who have been involved in the questionnaire study. This will take place after the questionnaire and patient participant interviews have been analysed.

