## **9.2. The Number of Participants**

Overall, a minimum of 300 participants will be required to complete the feasibility study. This is based on previous studies having used much smaller numbers to validate the SCQOLIT tool (8). This is a realistic sample size which can be recruited from the Dermatology Department; patient recruitment figures are derived from median numbers (+/- range) of patients seen in the Oxford Dermatology Department in 2013 with basal cell carcinoma (mean 160, range 140 – 172 / month) and squamous cell carcinoma (median 203, range 157 – 220 / month) obtained from a local departmental audit and the Skin Cancer Multidisciplinary Team Meeting IT data, respectively.

For the qualitative aspects of the study (Group 3) there will be a total of 20 volunteers interviewed (10 from each of Groups 1 and 2).

For Group 4 there will be 10-15 clinicians invited to the focus group.

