## 17. APPENDIX B: SCHEDULE OF STUDY PROCEDURES FOR GROUP 2 – CLINIC-BASED.

Procedures	Visits			
	Screening (Point of referral – first clinic visit)*	Baseline (within three weeks of being given a diagnosis of NMSC – verbal or postal)	3 months follow up	6 - 9 months follow up
Informed consent	Y (after being given PIS)	Y		
Demographics	Y			
Medical history	Y	Y		
Eligibility assessment (histological diagnosis of NMSC)	Y			
SCQOLIT questionnaire and EQ-5D questionnaire		Y	Y	Y (high risk SCC patients only)
Structured interviews				Y

\* This visit is applicable to all participants in the study including Group 1 (postal group)

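### Section 8 ties interviews to a follow-up appointment, against Sections 5, 7.2 and 7.4, which if followed would restrict Group 1 interviewees to patients who return; separately, Appendix B conflicts with the text on Group 2 interview timing

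*Combined protocol and SAP*

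**What the plan says.** **Setting.** Section 8 (Group 3: Interviews) lets the patient choose a suitable time but adds a condition: "when they attend Dermatology Outpatients for a follow-up appointment". Section 7.4 has a nearly identical sentence without that condition: "The interview will be undertaken at a time convenient to the patient in the Dermatology Outpatient Department". In Section 7.2 the qualitative researcher telephones the patient, and "a mutually agreed interview date will be arranged once the patient has consented verbally on the telephone". In Section 5, telephone consent is "confirmed face-to-face in written form when the patient attends the Dermatology department for the interview".

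**Group 1.** Section 7.4 describes the three-month contact for this group as "postal, for those patients discharged to community care". Section 9.2 plans 20 interviews, "10 from each of Groups 1 and 2". Sections 7.2 and 7.4 say that interviewees are chosen at random from those who gave their contact details.

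**Timing.** Sections 7.4 and 8 both put the interviews three to six months after study entry. Appendix B has a row for "Structured interviews" with one mark, in the 6–9 month column. That table is the Group 2 schedule, and its footnote extends only the screening visit to Group 1.

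**The concern.** For a patient who has been discharged, the rule in Section 8 and the rule in Sections 5, 7.2 and 7.4 give different answers. Under one the patient cannot be interviewed unless something else brings them back. Under the other they come in for the interview. Section 8 is the section that governs data collection, so it cannot be assumed that staff would disregard it.

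Analysis of patient and staff views is the second component of the mixed-methods primary endpoint (Sections 4 and 9.3). The ten Group 1 interviews are the only patient interviews planned for people who went through the postal route. If they come from a group selected by returning to clinic, the account of how acceptable that route is would be skewed. The timing conflict raises a similar selection question in Group 2, for a different reason.

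**Working it through.** No test or power calculation lies behind the interview number, so the check is simple arithmetic and a comparison of sections.

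**1. The plan's own figure.** Section 9.2: 10 + 10 = 20 interviews, which reproduces. The Group 1 share is 10/20 = 50%.

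**2. Where the interview takes place.**

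| Section | Rule | Follow-up appointment needed? |
|---|---|---|
| 5 | Patient attends the department for the interview | No |
| 7.2 | Date agreed by telephone | No |
| 7.4 | Department, at a time that suits the patient | No |
| 8 | At a follow-up appointment | Yes |

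**3. Who can be reached in Group 1.** Under Sections 5, 7.2 and 7.4, any Group 1 volunteer can be interviewed. The assurance in Section 7.4 that no extra visits are needed is limited to the questionnaire study, so it does not rule out a visit for the interview. Under Section 8, only those with a follow-up appointment qualify, and the text gives Group 1 no routine one. The return route it does describe is in Section 8: the Chief Investigator reviews postal responses and may arrange clinic follow-up where quality of life seems significantly impaired. Selection through that route would over-represent patients with worse quality of life. It would also be an extra filter on a sample already limited to volunteers.

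**4. Could ten still be found under Section 8?** The Group 1 share of the 300 participants is not stated. Assume 50% to 80%:
- 0.50 × 300 = 150 patients, and 10/150 = 6.7%
- 0.80 × 300 = 240 patients, and 10/240 = 4.2%

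So about 4% to 7% of Group 1 would have to volunteer, return and be interviewed. The documents do not show that this is impossible. Restricted selection is the likelier result.

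**5. Could the selection be seen afterwards?** Hardly. Section 8 records only gender and recruiting group for interviewees, and gives them a separate reference number so that interviews cannot be linked to questionnaires. Interviewees' scores could not then be compared with those of the rest of Group 1.

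**6. When the interview takes place.** If both windows count from study entry, three to six months and 6–9 months meet only at month 6. In Appendix B the questionnaire in the 6–9 month column is for high-risk SCC patients only (Section 7.4 adds rare NMSC). Group 2 as a whole is moderate to high risk (Section 6.1). An interview tied to that visit could therefore leave out Group 2 patients outside the high-risk subset.

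**The case against.** The strongest reply is that three sections agree with each other and one clause does not. Sections 5, 7.2 and 7.4 set out a workable process: random contact, telephone agreement on a date, and a visit for the interview. On that view the Section 8 clause is loose drafting, meant for patients who happen to have an appointment, and sensible staff would follow the fuller process. This stands as a limit on the consequence. It does not remove the contradiction, because Section 8 states its condition for both groups without exception.

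Several stronger readings are tempting, and the documents do not support them:

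- *The ten Group 1 interviews cannot be obtained.* The three other sections allow a separately arranged visit, and even under Section 8 the number needed is a small percentage of Group 1 on the assumed range.
- *Half the interviews, or all the evidence on the postal route, are lost.* Fifty per cent is an upper bound under the literal rule. Participation rates, response rates and missing values (Section 9.3) also bear on the postal route, as do recorded reasons for declining (Section 7.1).
- *The 6–9 month mark in Appendix B makes Group 1 harder to reach.* That table is the Group 2 schedule and says nothing about when Group 1 is interviewed.
- *An interview could colour a later questionnaire.* This could apply only to Group 2 interviewees who complete a third form, at most ten people, and the documents give no basis for sizing it.

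**Conclusion.** The plan contradicts itself in two places, and both matter modestly.

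First, the follow-up-appointment clause in Section 8 conflicts with Sections 5, 7.2 and 7.4 and does not fit a discharged Group 1. If it is followed, up to 10 of the 20 interviews would come only from returning patients, contrary to the random selection the plan promises. If the other sections are followed, none is affected.

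Second, and independently, Appendix B and Sections 7.4 and 8 give interview windows for Group 2 that share at most one month.

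This is an internal inconsistency with a possible selection bias in one component of the primary endpoint. It is not a design that prevents the interviews. The conclusion assumes that Group 1 has no routine clinic follow-up, which is what the text shows. The flow chart in Appendix A was not available to check this or the interview timing. It also takes the Appendix B mark to belong in the last column, as the table reads. The size of any bias cannot be estimated, because neither the Group 1 share nor the proportion who return is given.

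**What to change.** 1. In Section 8, delete the words "when they attend Dermatology Outpatients for a follow-up appointment" so that the sentence matches Sections 5, 7.2 and 7.4, and keep the department as the place.
2. State one interview window, counted from study entry, in Sections 7.4 and 8 and Appendix B. If the interview stays in a visit column, say whether it is open to all Group 2 patients or only to those attending that visit.
3. While editing Section 7.4, make its stopping rule for contacting patients say ten from each group, as Section 9.2 does. At present it can be read as ten in total.

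The cost is a wording amendment. The downside is that some Group 1 patients will make a visit solely for the interview, which Sections 5 and 7.4 already allow. Telephone interviews would spare them the journey, but they are optional, would need their own consent step, and are not required to resolve the contradiction.

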## 9. STATISTICS AND ANALYSIS

### 9.1. Description of Statistical Methods

As this is a feasibility study, both quantitative and qualitative data will be analysed. There will be no specific interim analyses of data but for Group 2, patients who complete the questionnaires in clinic will also have the chance to discuss their scores with their clinician (as described above). Clinicians will have the opportunity to feedback specific issues for individuals to the Chief Investigator and this will be recorded on the CRF. They will also have the opportunity to discuss general issues at the Staff focus group in the Dermatology Departmental Clinical Governance meeting.

Statistical analyses of PROM scores will be undertaken using Excel and SSPS software with statistical support from the Health Services Research Group, University of Oxford. Data reviewed will be in an anonymised form.

All interviews will be recorded using Olympus DSS digital recorder and transcribed verbatim by the researcher. A framework analysis, developed from the interview schedule and from themes that emerged during fieldwork, will be conducted using NVivo V.10 qualitative analysis software. All coding will be performed by the Qualitative Researcher.

